13.4.2. Efficacy Analyses

Efficacy endpoints will be summarized with descriptive statistics. The migraine and headache endpoints will be summarized by 4, 12, and 24 week intervals with the remaining endpoints being summarized by study week.

Primary Efficacy Analyses

Hypothesis testing will be performed for the primary endpoint: change in frequency of migraine days (Weeks 1-12). This endpoint will be calculated as outlined in Section 12.1.2 and will utilize the missing data rules provided in Section 13.3.2. Summary statistics including confidence intervals for the treatment differences will be used to summarize the results for the primary endpoint. Testing will also be employed. The hypotheses tested are

$$H_0: \Delta_{\text{plb}} = \Delta_{403}$$

$$H_a: \Delta_{\text{plb}} \neq \Delta_{403}$$

where Δ_{403} is the change in migraine days for subjects in the ALD403 treatment arm and Δ_{plb} is similarly defined for the placebo subjects. The change from baseline is expected to be negative as migraines are being reduced. While the test outlined above is two sided, as is the alpha level used for this study (i.e. 5%), clinically relevant results require a larger reduction of migraines on the ALD403 arms.

An ANCOVA model will be used to test for a difference between treatment arms. This model will include the change from baseline measure as the response variable. Treatment and the stratification variables: baseline migraine days (continuous predictor) and prophylactic medication use (use vs. no use) will be the independent variables.

Secondary Efficacy Analyses

Summary statistics including confidence interval for the treatment differences will be used to summarize the results for the secondary endpoints. Testing will be used for the key secondary endpoints. A CMH test controlling for the randomization stratification factors will be used for the responder rate key secondary endpoints, and the percent of subjects with a migraine on the day after dosing endpoint will be tested with an extended CMH test.¹⁵

The acute migraine medication day endpoint will be tested using an ANCOVA model similar to the one used for the primary endpoint. The time to first migraine analysis will be descriptively summarized based upon Kaplan-Meier methods.

The missing data rules provided in Section 13.3.2 will be used for the key secondary endpoints, except for the percentage (prevalence) of subjects with a migraine on the day after dosing endpoint. Subjects who did not complete the eDiary on the day following dosing will be included in the prevalence rate calculation based upon their Week 1-4 daily migraine rate. Hence, subjects with a migraine will be included in the rate calculation as a value of 1, subjects who completed the eDiary and did not have a migraine will be included as a 0, and subjects who did not complete the eDiary will be included with a value between 0 and 1 equal to their prevalence rate in Weeks 1-4 (i.e. the number of Weeks 1-4 migraine days divided by 28). The reduction in migraine prevalence from baseline to Week 4 endpoint will be difference in daily prevalence rates between Week 1 and baseline, Week 2 and baseline, and so on. The baseline daily prevalence will be calculated as the number of migraine days in baseline divided by 28. The Week 1 daily prevalence will be the number of migraine days in Week 1 divided by 7, with a similar definition for Weeks 2, 3, and 4. The same missing data approach for the day after dosing endpoint will be used for these weekly measures (i.e. any day the subject does not complete the diary will be assigned a value equal to the Weeks 1-4 prevalence rate). The treatment effect will be evaluated using a repeated-measures approach.¹⁶ The model will specify an unstructured variance/covariance matrix and include the treatment group, visit, baseline value of the outcome variable and treatment group-by-visit interaction. The Kenward-Roger approximation will be used to estimate the degrees of freedom. Pharmacokinetic Analyses

13.4.3. Analysis of Drug Concentrations

The concentrations of ALD403 will be listed and summarized by time point and dose group, and descriptive statistics will be provided. In this analysis, concentrations below the lower limit of quantification (LLOQ) will be set to zero.

Plots of the individual concentrations of ALD403 will be presented over time (linear and log scales). Plots of the mean or median concentration will be presented over time (linear and log scales). When the scale is linear, concentrations below the lower limit of quantification will be set to zero. In the log-scaled figures, concentrations below the LLOQ will be imputed as LLOQ/2. Population pharmacokinetic analysis will be performed on the results for ALD403 concentrations obtained during this study in combination with the results from other studies of ALD403 in normal subjects and migraine patients.

13.4.4. Safety Analyses

13.4.4.1. Adverse Events

The incidence of all AEs will be tabulated by treatment received. These AEs will be classified by system organ class and preferred term using the Medical Dictionary for Regulatory Activities (MedDRA). For incidence reporting, if a subject reported more than 1 AE that was coded to the same preferred term/system organ class, the subject will be counted only once for that specific preferred term/system organ class. Events recorded between the time the informed consent is signed and the first Investigational Product administration will be listed.

An overview of AEs, which includes subject incidence of AEs, SAEs, deaths, and AEs leading to discontinuation, will be presented. For AEs presented by severity, the worst severity during the clinical trial will be presented for each subject.

The subject incidence of AEs will be summarized by system organ class and preferred term.

13.4.4.2. Serious Adverse Events

All SAEs will be listed and summarized in a similar manner to AEs.

13.4.4.3. Clinical Laboratory Results

Summary statistics for actual values and for changes from baseline will be tabulated for clinical laboratory results by scheduled visit. Subjects with clinical laboratory values outside of the

normal reference range at any post-baseline assessment will be summarized. Shifts from baseline clinical laboratory values based upon the normal range and will be tabulated. Subjects developing an antibody response will be listed.

13.4.4.4. Electrocardiogram (ECG) Results

The observed data at baseline and change from baseline for each measurement day will be summarized with descriptive statistics.

13.4.4.5. Vital Signs

The observed data at baseline and change from baseline for each measurement day will be summarized with descriptive statistics.

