⁸ Vital signs measured pre-dose and within 2 hours post-dose on Days 0 and Week 12.

⁹ C-SSRS "Baseline/Screening Version" should be used at screening, and C-SSRS "Since Last Visit Version" should be used on Day 0 (pre-randomization), Weeks 2,4, 8, 12 (pre-dose), 16, 20, 24, and 32 or ET.

¹⁰ Inclusion/exclusion criteria review, C-SSRS, and urine pregnancy test must be done prior to dosing on Day 0. C-SSRS and urine pregnancy test must be done prior to dosing at Week 12.

¹¹ Conduct ECG pre-dose, and within 2 hours post dose on Day 0 and Week 12.

¹² Blood draws obtained pre-dose on dosing days (within 1 hour before dosing). On Day 0, draw additional PK immediately post dose (within 15 minutes of end of infusion). Subjects who test positive for anti-ALD403 antibodies at the last study visit will be asked to provide up to 2 additional blood samples for immunogenicity testing at 3 month intervals for up to 6 months.

¹³ Subjects must be monitored for at least 2 hours after the dosing completion to assess for the occurrence of adverse events. Subjects will be requested to stay longer than 2 hours after dosing should the investigator determine this is clinically warranted (e.g., subjects should be observed until all AEs are resolved or clinically stable).

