7.2. Clinical Trial Design

This is a parallel group, double-blind, randomized, placebo-controlled trial of two infusions of ALD403 or placebo in patients with chronic migraine. Subjects who provide informed consent will be evaluated for eligibility based upon the inclusion and exclusion criteria.

Eligible subjects will be randomized 28-30 days after the screening visit and treated (first dose) on Day 0, within 8 days after the randomization visit. Treatment includes two infusions of ALD403 or placebo administered on Days 0 and 84 (Week 12). Subjects will be followed for 20 weeks after the final dose for total study duration of approximately 36 weeks, including the screening period.

Approximately 1050 subjects will be randomized and treated. Efficacy, safety, pharmacokinetic, and immunogenicity assessments will be conducted according to the Schedule of Events presented in Section [2](#).

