13.3. General Considerations

13.3.1. Definition of Baseline

Baseline for migraine and headache endpoints will be based upon the data recorded in the headache eDiary during the 28-days following screening. For other variables, the baseline assessment will be the latest available valid measurement taken prior to the administration of Investigational Product. This will generally be Day 0.

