3.6.4. Vital Signs, Physical Findings and Other Observations Related to Safety

3.6.4.1. Vital Signs

The observed data at baseline and change from baseline for each measurement day will be summarized with descriptive statistics. A plot of average vital sign parameters will be presented over time.

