3.6.4.3. Electrocardiogram Results

The observed data at baseline and change from baseline for each measurement day will be summarized with descriptive statistics by treatment group.

The overall ECG assessment based upon PI assessment will be summarized including post treatment ECGs determined to be abnormal clinically significant.

The absolute QTcF values provided by the core lab will be analyzed as a categorical variable. Each QTcF value in a given patient will be grouped into 4 categories:

- QTcF interval < 450 msec
- QTcF interval 450 - 480 msec
- QTcF interval > 480 - 500 msec
- QTcF interval > 500 msec

The changes in QTcF measures will also be analyzed as categorical variables. The change in QTcF in a given patient will be grouped into 2 categories:

- QTcF interval increases from baseline > 30 msec
- QTcF interval increases from baseline > 60 msec

The overall ECG assessment will be summarized along with a summary of how many subject developed a post treatment abnormal clinically significant result. Denominators for percentages will use the number of assessments available at each visit.

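### No planned analysis measures the acute change in vital signs or ECG around the Week 12 infusion against that visit's own pre-dose reading, and the SAP visit-window rule may drop post-dose readings altogether

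*Protocol*

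**What the plan says.** **Timing.** Protocol Section 2, footnote 8: "Vital signs measured pre-dose and within 2 hours post-dose on Days 0 and Week 12". Footnote 11: "Conduct ECG pre-dose, and within 2 hours post dose on Day 0 and Week 12". Each infusion is therefore bracketed by two readings. Footnote 8 to SAP Table 1 also has vital signs before and after both infusions, but gives a 4-hour post-dose window where the Protocol gives 2 hours.

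**Baseline.** For variables outside the diary, Protocol 13.3.1 says "the baseline assessment will be the latest available valid measurement taken prior to the administration of Investigational Product", and adds: "This will generally be Day 0". SAP 3.2 agrees. Neither says the first administration in so many words, but the Day 0 remark implies one baseline per subject.

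**Change measures.** Protocol 13.4.4.4 (ECG) and 13.4.4.5 (vital signs) share one sentence: "The observed data at baseline and change from baseline for each measurement day will be summarized with descriptive statistics". SAP 3.6.4.1 repeats it for vital signs and adds: "A plot of average vital sign parameters will be presented over time". SAP 3.6.4.3 repeats it for ECG and adds change categories, the lower being "QTcF interval increases from baseline > 30 msec" and the upper 60 msec. All of these refer to baseline.

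**Visit windows.** SAP 2.4 defines trial day from dates alone. Table 3 keeps one non-diary value per window, the one nearest the target day. If two are equally near, the first is used.

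**The concern.** Safety of repeat doses against placebo is a secondary objective (Protocol 6.2), and Week 12 is the only re-dosing. Readings on either side of that infusion serve mainly to show what happens in the hours around it. The plan collects them but never takes the difference.

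Two things are at stake. First, if Table 3 is applied as written, the post-dose readings may not appear in the by-visit summaries for either infusion. Second, if they do appear, the Week 12 post-dose value is compared with a reading about 12 weeks old. An acute effect of re-dosing on blood pressure, pulse or QTcF is then combined with whatever else changed in between, and individual QTcF increases are flagged partly on that unrelated variation. SAP 3.6.2.1 defines infusion-associated adverse events by their time since dosing, so the plan does recognise dose-specific effects. The matching measurements get no such treatment at the second infusion.

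**Working it through.** The documents state no figure on this point, so there is nothing to reproduce. The check has two parts.

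**1. Which readings enter the by-visit summaries?** Trial day is assessment date minus treatment date. Pre-dose and post-dose readings on one date have the same trial day, so they are equally far from the target day (Day 0 or Day 84) and always tie. The tie rule selects the first, which is the pre-dose reading. Taken literally:

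- Day 0: the pre-dose value is kept. It is normally also the baseline, so the Day 0 change would be zero by construction.
- Week 12: the pre-dose value is kept, so its change from baseline describes the 12 weeks after dose one and says nothing about dose two.

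Neither document defines separate pre-dose and post-dose timepoints that would override this.

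**2. If post-dose readings are kept, what does the Day 0 reference measure?** The Week 12 change splits into two parts:

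(Week 12 post − Day 0 pre) = (Week 12 post − Week 12 pre) + (Week 12 pre − Day 0 pre)

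The first bracket is the acute change. The second holds general drift (common to all arms), any sustained effect of the first dose (active arms only) and visit-to-visit variation.

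With equal SD at each reading and correlation r between two readings, SD of change = SD × √(2(1 − r)). The SDs and correlations below are assumptions. The figure of 350 per arm is the planned size, with every subject assumed to have both readings.

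*QTcF, SD 18 msec, r = 0.8 at one visit and 0.6 over 12 weeks, normal changes with mean zero:*

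| | Same-visit reference | Day 0 reference |
|---|---|---|
| SD of change | 18 × √0.4 = 11.4 msec | 18 × √0.8 = 16.1 msec |
| P(increase > 30 msec) | P(Z > 30/11.4) = 0.0042 | P(Z > 30/16.1) = 0.0312 |
| Expected per 350 | 1.5 | 10.9 |

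*Range.* Over SD 15 to 20 msec and correlation pairs (same visit/12 weeks) from 0.9/0.7 to 0.7/0.5, chance increases above 30 msec run from 0 to 9 per 350 with the same-visit reference and from 2 to 23 with Day 0.

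*The 60 msec category.* With the Day 0 reference and SD of change 16.1 msec, chance gives about 0.03 per 350. At the top of the range, SD of change is 20 × √(2 × 0.5) = 20 msec, and P(Z > 3) = 0.00135 gives about 0.5 per 350.

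*Systolic pressure, SD 12 mm Hg, same correlations.* The SE of an arm difference is 12 × √0.4 × √(2/350) = 0.57 mm Hg against 12 × √0.8 × √(2/350) = 0.81 mm Hg. The 95% half-widths (1.96 × SE) are about 1.1 and 1.6 mm Hg.

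*In general.* For 12-week correlations of 0.5 to 0.7 and same-visit correlations of 0.8 to 0.9, the Day 0 reference makes the SD of change 1.22 to 2.24 times larger. If the two correlations are equal, the ratio is 1 and no precision is gained.

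**The case against.** A single pre-treatment baseline is a sound choice for repeat-dose safety because it captures cumulative effect. The tables are descriptive. Placebo subjects have the same 12-week gap, so average drift cancels between arms. Other routes to detection do not need a same-visit reference: SAP 3.6.4.3 also categorises absolute QTcF and summarises ECGs judged clinically significant, and SAP 3.6.2.1 lists blood pressure, heart rate and QT terms among events of special interest. The systolic half-widths, 1.1 against 1.6 mm Hg, are both small. If both Week 12 readings were tabulated, the mean acute change would follow by subtraction in subjects who have both.

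Most of this stands, and it limits the point to an addition to the tables. It does not remove the point. Subtracting means recovers neither the SD of the acute change nor the individual shifts above 30 msec. Placebo cannot separate an acute second-dose effect from a sustained first-dose effect, because placebo subjects have neither. Subtraction also needs both readings to be tabulated, which Table 3 as written does not provide.

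A reader might infer that the first infusion is measured by a clean before-and-after difference and the second on a different scale, so that outlier counts must look higher after the second infusion in every arm. The documents do not support that. Under the literal tie rule neither post-dose reading reaches the by-visit summaries. If both are kept, higher counts still require the 12-week correlation to be below the same-visit correlation, and the documents give neither.

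**Conclusion.** The gap is real. Every planned change measure for vital signs and ECG refers to one pre-treatment baseline, so no analysis measures the acute change at the only re-dosing against that visit's own pre-dose value. Read literally, SAP Table 3 goes further and leaves post-dose readings out of by-visit summaries at both infusions.

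If post-dose readings are kept, the cost is interpretability (acute and sustained effects combined) and, when the 12-week correlation is the lower one, precision. The assumed case gives 10.9 against 1.5 chance QTcF flags above 30 msec per 350. That size rests wholly on assumed SDs and correlations. Counts above 60 msec are hardly affected. A reader might also infer a biased comparison between arms. That does not follow: the Day 0 reference applies equally to all arms, and the arm difference remains a valid measure of total change since Day 0. This is a cheap improvement and does not threaten the trial's conclusions.

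**What to change.** Make these changes in SAP 2.4 (Table 3), 3.6.4.1 and 3.6.4.3, with matching text in Protocol 13.4.4.4 and 13.4.4.5:

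1. Define pre-dose and post-dose on Day 0 and at Week 12 as separate analysis timepoints for vital signs and ECG, exempt from the Table 3 tie rule.
2. Add, by treatment group and for both infusions, post-dose change from the same-visit pre-dose value. Apply the QTcF 30 and 60 msec categories to this change as well.
3. Keep change from the Day 0 baseline for cumulative effect, and state in the baseline definition that it refers to the first administration.
4. Reconcile the post-dose vital-sign window, which is 2 hours in Protocol Section 2 and 4 hours in SAP Table 1.

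Step 1 is needed for step 2 to work, because without it the post-dose values may not be in the summaries at all. The schedule already collects the readings. The cost is a few sentences and slightly longer descriptive safety tables.

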13.4.4.6. C-SSRS

The C-SSRS assesses lifetime suicidality during an initial baseline evaluation, and then monitors suicidal ideation and suicidal behavior at subsequent follow-up assessments. Four constructs are measured. The first and second are the severity and intensity of ideation, rated on a 5-point ordinal scale. The third is the behavior subscale, which is rated on a nominal scale and the fourth is the lethality subscale, which assesses actual attempts. These results will be reported at baseline and post baseline. Results for individual time points will be provided in a listing.

14. ETHICAL, LEGAL AND ADMINISTRATIVE ASPECTS

14.1. Data Quality Assurance

The Sponsor or designee will assess the site to verify the qualifications of each Investigator, according to Sponsor's or applicable SOPs. There will be an inspection of site facilities, and Investigator will be further informed of responsibilities and the procedures for ensuring adequate and correct documentation.

The Investigator is required to prepare and maintain adequate and accurate case histories designed to record all observations and other data pertinent to the clinical trial for each clinical trial subject. All information recorded on the CRFs for this clinical trial must be consistent with the subjects' source documentation (i.e., medical records).

14.2. Case Report Forms and Source Documents

As part of the responsibilities assumed by participating in the study, the principal investigator or sub-investigator agrees to maintain adequate case histories for the patients treated as part of the research under this protocol. The principal investigator or sub-investigator agrees to maintain accurate eCRFs and source documentation as part of the case histories. These source documents include, but are not limited to, laboratory reports and original ECGs.

14.3. Study Documentation

Source document is defined as any hand written or computer generated document that contains medical information or test results that have been collected for or are in support of the protocol specifications, e.g., clinical laboratory reports, clinic notes, drug disbursement log, subject sign in sheets, subject completed questionnaires if applicable, telephone logs, ECGs, etc. All draft, preliminary and pre-final iterations of a final report are also considered to be source documents, e.g., faxed laboratory reports and hard copy laboratory reports, faxed initial results and hard copy, final report.

14.4. Data Collection and Electronic Data Capture (EDC)

The data collected during the study (except clinical laboratory test results, eDiary results, ECG results, PK analyses, Immunogenicity) will be recorded in the subject's eCRF. The Short-Form Health Survey (SF-36), Health related Quality of Life (EQ-5D-5L), Headache Impact Test (HIT-

6), Patient Global Impression of Change (PGIC), Most Bothersome Symptom (MBS) and C-SSRS will be completed on paper forms and then entered into the EDC system. The study site(s) will use an EDC system that is compliant with relevant Food and Drug Administration (FDA) regulatory requirements per 21 CFR Part 11. Data queries and data corrections will be handled through the same system. All transactions within the EDC system are fully documented within an electronic audit trail. Each set of completed eCRFs must be reviewed after being source verified by monitor and electronically signed and dated by the Investigator.

14.5. Archiving Clinical Trial Records

According to ICH guidelines, essential documents should be retained for a minimum of 2 years after the last approval of a marketing application in an ICH region and until there are no pending or contemplated marketing applications in an ICH region or at least 2 years have elapsed since the formal discontinuation of clinical development of the Investigational Product. However, these documents should be retained for a longer period if required by applicable legal requirements.

It is the responsibility of the Investigator and clinical trial staff to maintain a comprehensive and centralized filing system of all clinical trial-related documentation. This centralized file should be available for inspection at any time by the Monitor or Quality Assurance staff for monitoring or auditing by Alder BioPharmaceuticals, Inc. and regulatory authorities. Elements of clinical trial documentation should include:

- Subject files containing the completed CRFs supporting source documentation and the signed ICF
- Clinical trial files, containing the protocol with all amendments, the Investigator Brochure, copies of all clinical trial documentation, and all correspondence to and from the ethics committee and Alder BioPharmaceuticals, Inc.
- Pharmacy files, containing the Investigational Product Accountability Records or dispensation logs and all clinical trial agent-related correspondence

